11.5 Sample Size Determination

Our primary objective is to use EMCAT to compare the recovery trajectories of patients undergoing PNF and LF for Dupuytren's disease. To have a 90% chance of detecting a moderate effect size of 0.35 between groups on a z-score scale (with a standard deviation of 1), at the 5% significance level, 344 patients are required for each comparison (172 per group). Assuming a 15% attrition, this leaves a target sample size of 396 for the primary objective (198 per group).

Objective 2 (see section 6) sets out 4 more comparisons, involving 7 other groups of patients:

- Steroid injection for TBOA
- Steroid injection for trigger finger
- Trapeziectomy for TBOA
- Arthroplasty for TBOA
- Surgical release of trigger finger
- Open carpal tunnel decompression
- Minimally invasive (endoscopic or percutaneous) carpal tunnel decompression

At 198 participants per group, and 9 groups total, a further 1386 participants (1782 total) would be required to reach statistical significance in all of our secondary (non-essential) objectives. We will recruit as many participants as we can in these groups, within the limits of the study timing and funding, and up to a maximum of 198 per group.

In summary, our recruitment target is 396 (172 participants undergoing LF and 172 participants undergoing PNF), but we will recruit up to a maximum of 1782 participants (198 in each of the groups described above).

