6. OBJECTIVES AND OUTCOME MEASURES

Objectives	Outcome Measures	Timepoint(s) of evaluation of this outcome measure (if applicable)
Primary Objective		
1. Compare the recovery trajectories of patients undergoing percutaneous needle fasciectomy (PNF) to patients undergoing limited fasciectomy (LF), to test whether EMCAT can detect different recovery trajectories over a 12-week period, with less severe post-treatment symptoms in the PNF group within the first 4 weeks.	The PEM, administered via EMCAT.	Trajectories will be plotted and compared over a 12-week period.
Secondary Objectives		
2. Compare the recovery trajectories of other groups that are expected to differ over a 12-week period. Specifically, we will test the following hypotheses, which are based on the researchers' clinical experience:	The PEM, administered via EMCAT.	Trajectories will be plotted and compared over a 12-week period.
 Steroid injection results in less severe post-treatment symptoms than trapeziectomy, within the first 4 weeks 		
 Trapeziometacarpal arthroplasty results in less severe post- treatment symptoms than trapeziectomy, within the first 4 weeks 		
 Minimally invasive (endoscopic or percutaneous) CTD results in less severe post-treatment symptoms than open CTD, within the first 2 weeks 		
 The difference in the recovery of groups undergoing open release vs steroid injection for trigger finger are not clinically significant over the first 2 weeks 		
The objective is to test EMCAT's ability to differentiate between recovery trajectories that are expected to differ, rather than to prove or disprove that differences in recovery trajectory exist. The clinical comparisons are a vehicle for testing the measurement properties of EMCAT. Here, the threshold for clinically significant difference is approximated as half a standard deviation of baseline scores of groups being compared. Statistical significance is taken at the 5% level. By symptom severity, we mean PEM EMCAT scores, where a higher (poorer) score reflects more severe symptoms (a poorer level of hand health).		

	UES scores,	12-week follow-up
3. Assess the usability of the EMCAT platform	response rates, response times, and semi- structured interviews	
4. Assess the criterion validity of EMCAT against the full-length PEM by comparing scores at baseline, 6 weeks, and 12 weeks	Full-length PEM scores and EMCAT PEM scores	Baseline, 6-week and 12-week follow-up
Exploratory Objectives		

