11.4 Description of the Statistical Methods

The hypotheses outlined in the primary and secondary objectives will be tested with mixed-effects linear modelling. These models will comprise: EMCAT score (continuous dependent variable on a logit scale, derived from a graded response model); participant number (random intercept); age, sex, and baseline score (fixed effects); and an interaction term between time (number of days following the intervention) and treatment allocation. Marginal means will be derived from these models and between-group differences calculated at daily timepoints after Tukey adjustment for multiplicity. This will be performed with the *emmeans* R package, or equivalent software. For each comparison, marginal means will be plotted, and differences compared to a minimal important difference (MID) estimate of half a standard deviation of baseline scores. Clinically and statistically significant (at the 5% level) differences will be compared to those predicted (see section 6).

EMCAT completion rates (number of completed response sets divided by number of invitations), response times, and UES scores will be analysed through descriptive statistics. The UES was originally intended to measure 6 user engagement constructs, but subsequent studies have suggested that it follows a 4-factor structure. Items of the UES will be grouped into the 4 subscales described by O'Brein et al, to measure: focused attention, aesthetic appeal, perceived usability and reward⁵.

The criterion validity of the EMCAT scores against the full-length PEM scores will be assessed by comparing pairs of EMCAT scores and full-length PEM scores that were obtained from the same participant on the same day. Comparison will be made by calculating Pearson's correlation coefficient, mean absolute error, root mean squared error and the Bland-Altman method⁶.

In Stream 2, three independent clinicians will review EMCAT trajectories (presented as time series plots) and follow-up appointment dates for participants that underwent open CTD. They will be asked to predict whether a change in management was required at the follow-up appointment. We will calculate inter-rater reliability of these assessments (Fleiss' kappa) and, for each clinician, the accuracy, sensitivity, specificity, positive predictive value and negative predictive value of their predictions against the reference standard (whether or not the patient received a change in management).

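### The 90% power covers statistical significance at 0.35 SD, but Section 11.4 reads results against a clinical threshold of 0.5 baseline SD, which lies above the design effect

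*Protocol*

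**What the plan says.** Section 11.5 sets the sample size: "To have a 90% chance of detecting a moderate effect size of 0.35 between groups on a z-score scale". The calculation takes the SD as 1 and tests at 5%. This gives 172 per group (344 per comparison), raised to 198 per group for attrition.

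Section 6 adds a second yardstick: "the threshold for clinically significant difference is approximated as half a standard deviation of baseline scores of groups being compared". Section 11.4 repeats it as the minimal important difference (MID) for every comparison, and then says how results are read: "Clinically and statistically significant (at the 5% level) differences will be compared to those predicted". The predictions are those of Section 6. Four of them (the primary comparison and three secondary ones) predict milder symptoms in one group within the first 4 or 2 weeks. The fifth, for trigger finger, predicts a difference that is not clinically significant.

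The protocol does not relate 0.35 to 0.5 and gives no probability of reaching the 0.5 threshold. Section 11.3 says that no separate analysis plan is in use, so the protocol is where the reading of the results is fixed.

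**The concern.** The effect the study is powered to detect is, by the protocol's own threshold, too small to be clinically significant. If the true PNF versus LF difference were 0.35 SD, the usual result would be a significant test with an estimate below 0.5 SD. The study exists to judge whether EMCAT picks up differences that are expected. Under the most direct reading of Section 11.4, that result is not among the differences set against the predictions, so a correctly detected difference could be scored as a failure of the instrument. Under a looser reading it counts as success. The choice should be made before the data are seen.

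Comparing a point estimate with 0.5 also takes no account of its uncertainty. A study whose true difference equals the MID exactly would pass or fail as on a coin toss.

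**Working it through.** **Inputs.** From Section 11.5: δ = 0.35, SD = 1, power 90%, level 5%, 172 per group, 198 recruited per group, 15% attrition. From Sections 6 and 11.4: threshold 0.5 baseline SD. Assumed: a two-sided test, one between-group contrast, normal approximation and, at first, baseline SD equal to the sizing SD.

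**The plan's own figure.** n per group = 2 × (1.960 + 1.2816)² / 0.35² = 2 × 10.508 / 0.1225 = 171.6, so 172 per group and 344 in all. This reproduces. A one-sided test would need 140, so the calculation is two-sided. With SE = √(2/172) = 0.1078, power at 0.35 is Φ(0.35/0.1078 − 1.960) = Φ(1.286) = 90.1%.

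**Which criterion binds.** Significance needs an observed difference of 1.960 × 0.1078 = 0.211 SD. The clinical threshold is 0.5 SD, so it alone decides whether both criteria are met.

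**Chance of meeting both.** P = 1 − Φ((0.5 − δ)/SE).

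| True difference (SD) | Significance alone | Both criteria |
|---|---|---|
| 0.35 | 90.1% | 1 − Φ(1.391) = 8.2% |
| 0.50 | 99.6% | 50% |
| 0.60 | over 99.9% | 82% |
| 0.64 | over 99.9% | 90% |

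The 90% point is 0.5 + 1.2816 × 0.1078 = 0.638 SD. At a true 0.35 SD the joint figure is 8.5% with 168 per group (198 × 0.85 = 168.3) and 6.8% with 198.

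**Effect of sample size, equal SDs.** At a true 0.35 SD the joint chance is 14% with 100 per group, 8% with 172 and 1.7% with 400. It falls because a tighter estimate is less likely to stray above 0.5. At a true 0.5 SD it stays at 50%, as long as the SE is small enough for 0.5 to remain the binding criterion.

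**Sensitivity to the SD assumption.** Section 11.5 does not say that its SD of 1 is the baseline SD. Let k = baseline SD / outcome SD. The threshold is then 0.5k in outcome SDs, and P = 1 − Φ((max(0.5k, 0.211) − 0.35)/0.1078).

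| k (assumed) | Threshold | Both criteria at a true 0.35 |
|---|---|---|
| 0.6 | 0.30 | 68% |
| 0.7 | 0.35 | 50% |
| 0.8 | 0.40 | 32% |
| 1.0 | 0.50 | 8% |
| 1.2 | 0.60 | 1% |

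The joint rule keeps the 90% only if 0.5k ≤ 0.211, that is, k of about 0.42 or less.

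**Baseline adjustment.** The model adjusts for baseline score. With an assumed correlation of 0.3 to 0.7, SE is multiplied by √(1 − ρ²), and the joint chance at 0.35 (k = 1) becomes 7% to 3%.

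**The case against.** The best defence is that nothing in Section 11.5 is false. It gives 90% for detecting 0.35 SD at the 5% level, and that is right. Powering below the MID is cautious for the significance test: at a true 0.5 SD, power is 99.6%. Section 11.4 opens by saying that the mixed model tests the hypotheses, and the later comparison with the MID can be read as descriptive. The primary hypothesis asks only for milder symptoms after PNF and names no minimum size. And 0.35 is a size to be detectable, not a forecast.

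All of this stands, and it rules out several stronger conclusions that a reader might draw:

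- *That the sample size or the 90% is wrong.* It is not. The protocol never claims 90% for the combined criterion.
- *That the planned analysis has 8% power.* The 8% belongs to one contrast under equal SDs. The plan calculates daily contrasts, and the chance that some day passes depends on a between-day correlation that the protocol does not give, so no figure can be put on it.
- *That the result would be undecidable.* If the joint rule applies, a significant difference below 0.5 SD simply does not meet it. If it does not apply, the test decides. The difficulty is that the text leaves room for both readings.
- *That more participants are needed.* With equal SDs, a larger sample lowers the joint chance at 0.35 SD.

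The defence does not remove the wording of Section 11.4, which joins the two criteria in its only statement of how results are set against the predictions.

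**Conclusion.** The point holds as a mismatch between sections, not as an arithmetic error. The stated power concerns significance at 0.35 SD, whereas the stated reading of results also asks for 0.5 baseline SD. Taken as a joint rule on a single contrast with 172 per group and equal SDs, it would be met about 8% of the time at the design effect and 50% at the MID, and 90% only at about 0.64 SD. The 8% depends strongly on the SD ratio: 68% to 1% for ratios of 0.6 to 1.2. Throughout that assumed range it stays below the 90% that a reader might carry over from Section 11.5. In practice, true differences between about 0.21 and 0.5 SD are at stake. They can be shown statistically, yet could be counted as EMCAT missing a difference that it found. This should be settled before analysis.

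**What to change.** In Section 11.4, state that the four hypotheses predicting milder symptoms are decided by the statistical test of the between-group difference over the hypothesised window (4 or 2 weeks). That contrast has to be written down, because the section currently names only daily differences. Report its 95% CI against 0.5 baseline SD (wholly above, straddling or wholly below) as interpretation only. State separately that the trigger-finger hypothesis, which is about the absence of a clinically significant difference, is judged by its CI against 0.5 SD.

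In Section 11.5, add that the 90% refers to statistical significance only and does not cover reaching the 0.5 SD threshold. If the 8% or 0.64 SD figures are quoted there, they need their assumptions beside them (one contrast, 172 per group, baseline SD equal to the sizing SD).

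The cost is two or three sentences and a less favourable statement about the clinical threshold. Recruitment does not change.

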7. STUDY DESIGN

We will perform a mixed-methods cohort study to explore the feasibility of EMCAT for measuring between-group differences in postoperative recovery, its potential to guide follow-up type (face-to-face, telemedicine or patient-initiated) in open carpal tunnel decompression, and its potential to guide follow-up timing after steroid injection for TBOA. The study setting will be NHS hospitals in the England, Scotland and Wales.

Our primary objective is to use EMCAT to compare the recovery trajectories of patients undergoing PNF and LF for Dupuytren's disease. We expect to see a difference in recovery trajectory over a 12-week period, with patients undergoing PNF showing less severe symptoms than those undergoing LF over the first 4 weeks. To meet this objective, we will recruit 396 participants (198 undergoing PNF and 198 undergoing LF), who will be followed up for a 12-week period with daily EMCAT assessments.

To address our secondary objectives, we will simultaneously recruit patients undergoing:

- Steroid injection for TBOA
- Steroid injection for trigger finger
- Trapeziectomy for TBOA
- Arthroplasty for TBOA
- Surgical release of trigger finger
- Open CTD
- Minimally invasive (endoscopic or percutaneous) CTD

We will recruit as many participants as we can in these groups, within the limits of the study timing and funding, and up to a maximum of 198 per group. We will use all collected EMCAT data to test the following hypotheses:

- Steroid injection results in less severe post-treatment symptoms than trapeziectomy, within the first 4 weeks
- Trapeziometacarpal arthroplasty results in less severe post-treatment symptoms than trapeziectomy, within the first 4 weeks
- Minimally invasive (endoscopic or percutaneous) CTD results in less severe post-treatment symptoms than open CTD, within the first 2 weeks
- The difference in the recovery of groups undergoing open release vs steroid injection for trigger finger are not clinically significant over the first 2 weeks

The objective is to test EMCAT's ability to differentiate between recovery trajectories that are expected to differ, rather than to prove or disprove that differences in recovery trajectory exist. The clinical comparisons are a vehicle for testing the measurement properties of EMCAT.

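### The primary recruitment target of 396 is split as 172 + 172 in one place and 198 + 198 elsewhere, and the 15% attrition allowance is slightly too small

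*Protocol*

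**What the plan says.** Section 11.5 starts from the design values: "To have a 90% chance of detecting a moderate effect size of 0.35 between groups on a z-score scale", "on a z-score scale (with a standard deviation of 1"). The number before attrition follows: "at the 5% significance level, 344 patients are required for each comparison (172 per group"). The allowance for loss comes next: "Assuming a 15% attrition, this leaves a target sample size of 396 for the primary objective (198 per group").

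The last paragraph of the section restates the target: "our recruitment target is 396 (172 participants undergoing LF and 172 participants undergoing PNF"). The same sentence caps every treatment group at 198, for a maximum of 1782.

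Section 7 agrees with the first statement and not with the last: "we will recruit 396 participants (198 undergoing PNF and 198 undergoing LF"). The synopsis also gives 396 for the primary objective. Section 11.3 says that no separate SAP document is in use, so this text is the study's statement of its sample size.

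**The concern.** Two things look wrong.

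- **The split.** The closing sentence breaks 396 into two groups of 172. They do not add up to 396, and they disagree with the 198 per group in the same section and in Section 7. Taken literally, the split removes the attrition allowance that the section has just added.
- **The allowance.** Going from 172 to 198 adds 15% of the evaluable number. Attrition is a fraction of those recruited, so the evaluable number should be divided by the fraction retained. Adding 15% gives too few.

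At stake are the recruitment target for the study's one fully targeted comparison and the power claimed for it. Both are figures that sites and later readers will take from the protocol.

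**Working it through.** **Inputs (Section 11.5):** standardised difference 0.35, SD 1, significance level 5%, power 90%, attrition 15%. Equal group sizes are given in Section 7. The sidedness of the test is not stated. Two-sided is inferred because it reproduces the protocol's figure; one-sided gives 140 per group and does not.

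**1. Reproduce the number before attrition.**
n per group = 2 × (1.960 + 1.2816)² / 0.35² = 171.5, rounded up to 172, or 344 in total. This matches. The t-test version gives 172.5.

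**2. Reproduce the attrition step.**
172 × 1.15 = 197.8, so 198. Likewise 344 × 1.15 = 395.6, so 396. Both match, so the allowance was a multiplication by 1.15.

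**3. The allowance that would keep 172.**
172 / (1 − 0.15) = 172 / 0.85 = 202.4, so 203 per group and 406 in total. Inflating the total directly gives 344 / 0.85 = 404.7, so 405. The stated 396 is 9 to 10 short, about 2.5%.

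**4. The loss that 198 per group covers.**
1 − 172/198 = 0.131, or about 13%.

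**5. Power at 198 per group if 15% contribute nothing.**
198 × 0.85 = 168.3 per group. Normal approximation: power = Φ(0.35 × √(168.3/2) − 1.960) = 89.4%. The t-test gives 89.3% at 168.3 per group and 89.2% at 168. The shortfall from 90% is about 0.6 points by the normal approximation.

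**6. Check the closing sentence.**
172 + 172 = 344, and 396 − 344 = 52, which is the whole attrition allowance. By contrast 198 + 198 = 396 and 9 × 198 = 1782, which agree with every other total in the protocol.

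**7. Only if 172 per group were mistakenly taken as the recruitment target.**
172 × 0.85 = 146.2 per group. Power = Φ(0.35 × √(146.2/2) − 1.960) = 84.9% (84.7% by t-test), about 5 points below 90%.

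| Recruited per group | Left after 15% complete loss | Power, normal | Power, t-test |
|---|---|---|---|
| 198 (Section 7; 11.5 main text) | 168.3 | 89.4% | 89.3% |
| 172 (11.5 closing split, if used) | 146.2 | 84.9% | 84.7% |

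**The case against.** The strongest reply is that neither error changes the study.

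- **The intended target is clear.** The sentence with the wrong split also gives the total as 396 and the cap as 198 per group, and the source of 172 is stated in the same section. A reader might infer that sites would close each primary group at 172. Nothing in the protocol sets such a rule, and it would mean ignoring the 396 in that very sentence. This stands: the 85% figure describes a misreading, not the plan.
- **A full 15% loss is a pessimistic case.** Section 9.10 aims to replace withdrawn participants during the recruitment period and allows data collected before withdrawal to be kept. Section 11.6 includes everyone enrolled unless withdrawn, and Section 11.10 fits the primary models to whatever data exist. The directional hypothesis concerns the first 4 weeks, so someone who stops later has already supplied data for that window. Most of this stands. It is not a complete answer: Section 9.10 also lets participants remove all their data, excludes those withdrawn by the investigator before analysis begins, and offers replacement only as an aim. Some losses can therefore be total, and the protocol itself chose to inflate for 15%.
- **The seven other groups have no required number.** A reader might carry the shortfall of five per group across all nine groups. Section 11.5 recruits the other seven as far as time and funding allow, under a cap and for objectives it calls non-essential. There is no target there to fall short of, so the point is confined to the primary comparison.

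**Conclusion.** Both statements in Section 11.5 are wrong as written, and both are minor. The closing split contradicts its own total and Section 7. The attrition allowance was calculated by multiplying by 1.15 instead of dividing by 0.85, so 198 per group protects 90% power against about 13% loss, not 15%.

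A reader might infer that the study fails to deliver its stated power. The documents do not support that reading. At the 396 that the protocol otherwise gives consistently, power is about 89.4% (89.2–89.3% by t-test) even if 15% contribute nothing, and partial data or replacement would bring it closer to 90%.

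These figures rest on a two-sided 5% test, equal groups, the protocol's own effect size and SD, and a simple comparison of two means, which is the calculation that reproduces 172.

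**What to change.** In the closing sentence of Section 11.5, change the split to 198 LF and 198 PNF so that it agrees with 396 and with Section 7.

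In the same section, restate the attrition sentence in one of two equivalent ways: 396 gives about 89% power if 15% contribute no data, or 396 gives 90% power with attrition of about 13%. Saying that the test is two-sided would let a reader reproduce 172.

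The cost is wording and a power figure about one point less favourable; no extra patients are needed. If the team prefers to keep both 90% and 15%, the target becomes 203 per group (406), and the cap of 198 and the totals in Section 11.5, Section 7 and the synopsis would have to be revised to match. The small shortfall does not require that.

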11.6 Analysis populations

All participants as enrolled will be included in the analysis unless withdrawn.

11.7 Decision points

No interim analyses are planned.

11.8 Stopping rules

No stopping rules are planned.

11.9 The Level of Statistical Significance

Clinical Research Protocol Template version 15.0

CONFIDENTIAL

© Copyright: The University of Oxford and Oxford University Hospitals NHS Foundation Trust 2019 Page 24 of 33 Statistical significance will be defined at the 5% level.

11.10 Procedure for Accounting for Missing, Unused, and Spurious Data.

Data which are clearly spurious will be excluded. Missing data will be described. For each variable, the association of missingness and the values of other variables will be analysed through descriptive statistics. All available data will be used to fit the models used for the primary analysis. We will not impute missing data and do not plan to undertaken any sensitivity analyses.

